### 9.1.1. Adverse Events Summaries

The number and percentage of participants with AEs will be summarized by SOC and PT. This summary will further be tabulated by strongest relationship to study intervention (related: definitely, probably, and possibly related; unrelated: unrelated; missing). A similar summary of TEAEs will be produced by maximum intensity (mild, moderate, severe, missing). In addition, the number and percentage of participants who experienced non-serious TEAEs (all TEAEs except serious TEAEs) that occurred in more than 5% of participants in either treatment group will be presented by SOC and PT for each treatment.

To count the number of participants who experienced each TEAE, a participant experiencing the same TEAE multiple times will only be counted once for the corresponding PT. Similarly, if a participant experiences multiple TEAEs within the same SOC, the participant will be counted only once for that SOC. For summaries by maximum severity, if a participant experiences more than one TEAE with different intensities severity (e.g., the same SOC and PT), only the worst intensity/severity will be reported. If a participant has both missing and non-missing intensity for a given SOC and PT, the missing intensity is selected for reporting unless the non-missing severity is noted as Severe. Treatment-emergent AEs will be sorted alphabetically by SOC and PT and presented by decreasing order of overall frequency. Treatment-emergent AEs analyzed by strongest relationship will be selected similarly for participants experiencing more than one TEAE with different relationships. If a participant has both missing and non-missing relationship for a given SOC and PT, the missing relationship is selected for reporting unless the non-missing relationship is noted as Related.

The number of TEAEs will be presented by SOC and PT. The total number of TEAEs will also be presented in the display.

In addition, all TEAEs will be provided in a listing, which will include the participant identifier, study intervention start date/time, SOC, PT, verbatim term, intensity, seriousness, relationship, action taken, outcome, date/time of onset, study day, date/time of resolution, and event duration in days. Event duration will be calculated as: (resolution date – start date) +1.

### 9.1.2. Summaries for Serious Adverse Events, AEs Resulting in Early Withdrawal, and Deaths

The number and percentage of participants who experienced treatment-emergent SAEs will be presented by SOC and by PT within each SOC. Treatment-related treatment-emergent SAEs, TEAEs resulting in treatment withdrawal from the study, TEAEs will be presented similarly in separate analyses.

Moreover, the number of SAEs (as opposed to the number and percentage of participants) and TEAEs resulting in early withdrawal from the study will be presented by SOC and PT within SOC.

Listings by participant for serious adverse events, deaths, and TEAEs resulting in early withdrawal will be generated.

### 9.1.3. Other Significant Adverse Events

Adverse events of special interest (AESI) will be summarized and include injection site reactions, muscle pain or weakness, and kidney stone events.

An injection site reaction is a disorder characterized by an intense adverse reaction (usually immunologic) developing at the site of an injection. Potential ISRs will be graded as follows:

Individual signs or symptoms at the injection site (e.g., erythema, swelling, etc.) reported within 4 hours of study intervention administration will be recorded as AEs at injection site (not as an injection site reactions) and graded in accordance with the intensity categories detailed in Section 9.1.1.

After 4 hours post dose, signs or symptoms at the injection site will be evaluated according to the Common Terminology Criteria for Adverse Events (CTCAE; Version 5.0) criteria for injection site reactions.

Because the nonclinical safety program in mice identified potential off-target effects on skeletal muscle, participants will also be monitored for signs and symptoms of muscle weakness or pain, and plasma creatine kinase measurements.

Participants with PH are predisposed to the development of multiple and recurrent urinary tract and kidney stones. Stone events, while being considered in the evaluation of efficacy, will also be considered AESIs.

Injection site reactions and treatment-emergent signs of muscle weakness or pain will be summarized by SOC and PT using the methods described in Section 9.1.1. Summaries for these events by maximum severity, as described in Section 9.1.1, will also be produced. However, summaries by maximum intensity for injection site reactions >4 hours postdose will be based on CTCAE grading criteria (Grades 1 through 5; where Grade 1 is least severe and Grade 5 is most severe) for injection site reactions. If a participant has both missing and non-missing missing CTCAE grades for a given SOC and PT, the missing CTCAE grade is selected for reporting unless the non-missing CTCAE grades is noted as Grade 4 or Grade 5. Kidney stone events will be summarized by the specific kidney stone event type that is collected on the adverse event

CRF: renal stone requiring medical intervention, stone passage with or without hematuria, and renal colic requiring medication. Kidney stone events will also be summarized by maximum severity.

By-participant data listings for injection site reactions, treatment-emergent signs of muscle weakness or pain, and treatment-emergent kidney stones will be provided.

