10.3.3. Definition of Adverse Event of Special Interest

An AESI is a noteworthy event for the particular product or class of products that a Sponsor may wish to monitor carefully ([CIOMS VI, 2005](#)).

Events Meeting the AESI Definition:**Injection site reaction (ISR):**

An ISR is a disorder characterized by an intense adverse reaction (usually immunologic) developing at the site of an injection. Potential ISRs will be graded as follows:

Signs or symptoms at the injection site (e.g., erythema, swelling) with a time to onset of 4 or more hours from the time of study intervention administration will be evaluated according to the Common Terminology Criteria for Adverse Events (CTCAE) v 5.0 criteria for ISR, detailed below. If any of the CTCAE criteria for ISR are met, the event will be recorded as an ISR and graded in accordance with **Table 4**. If the criteria are not met, individual signs or symptoms will be recorded as AEs and graded in accordance with the intensity categories detailed in Section 10.3.4.

Table 4: Grading of Injection Site Reactions, CTCAE v 5.0

Grade 1	Grade 2	Grade 3	Grade 4	Grade 5
Tenderness with or without associated symptoms (e.g., warmth, erythema, itching)	Pain; lipodystrophy; edema; phlebitis	Ulceration or necrosis; severe tissue damage; operative intervention indicated	Life-threatening consequences; urgent intervention indicated	Death

Individual signs or symptoms at the injection site with a time to onset of less than 4 hours from the time of study intervention administration will be recorded as AEs (not as an ISR) and graded in accordance with the intensity categories detailed in Section 10.3.4.

Muscle pain or weakness

Because the nonclinical safety program in mice identified potential off-target effects on skeletal muscle, participants should be monitored for signs and symptoms of muscle weakness or pain, in addition to measurement of plasma CK.

Kidney Stone Events

Patients with PH are predisposed to the development of multiple and recurrent urinary tract and kidney stones. As participants may enter the study with pre-existing stones, stone events (as defined in Section 8.1.6.1), while being considered in the evaluation of efficacy, will be considered AESI.

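### SAP 9.1.3 lets an ungraded injection site reaction displace a recorded Grade 3 in the maximum-grade table

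*SAP*

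**What the plan says.** SAP 9.1.3 names ISRs as adverse events of special interest and asks for a summary by maximum severity following the methods of 9.1.1. For reactions more than 4 hours after dosing, the scale is CTCAE: "Grades 1 through 5; where Grade 1 is least severe and Grade 5 is most severe". A tie-break covers participants with some grades missing. It opens "If a participant has both missing and non-missing missing CTCAE grades for a given SOC and PT" and concludes that "the missing CTCAE grade is selected for reporting unless the non-missing CTCAE grades is noted as Grade 4 or Grade 5".

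SAP 9.1.1 sets the general rule for maximum-severity tables. When one participant has events of differing severity, "only the worst intensity/severity will be reported". Its own tie-break for missing values is that "the missing intensity is selected for reporting unless the non-missing severity is noted as Severe". Missing is a displayed category there: "A similar summary of TEAEs will be produced by maximum intensity (mild, moderate, severe, missing".

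Protocol 10.3.3, Table 4, gives the content of Grade 3 for an ISR: "Ulceration or necrosis; severe tissue damage; operative intervention indicated". SAP 6.1.10.1 states that AE intensity is not imputed.

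**The concern.** A maximum-grade table should show, for each participant, the worst reaction known to have occurred. If a participant has a recorded Grade 3 ISR, the true maximum is at least Grade 3 whatever the ungraded reaction was. Moving that participant to the missing row replaces a known lower bound with no information, and the Grade 3 row is then one too low. Because intensity is not imputed, no later step restores the grade.

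At stake is the severity profile of a named special-interest event in the table where readers will compare the two arms. No efficacy endpoint, hypothesis test or type I error is involved.

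**Working it through.** The plan gives no figure to reproduce. The check is to apply the 9.1.3 rule to each possible pair of one ungraded and one graded ISR in the same participant, SOC and PT, and compare the result with the worst recorded grade.

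| Recorded grade, alongside one missing | Reported under 9.1.3 | Worst recorded | With Grade 3 added to the exception |
|---|---|---|---|
| 1 | missing | 1 | missing |
| 2 | missing | 2 | missing |
| 3 | **missing** | **3** | **3** |
| 4 | 4 | 4 | 4 |
| 5 | 5 | 5 | 5 |

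The 9.1.1 rule for ordinary TEAEs, applied in the same way, gives: mild with missing is reported as missing; moderate with missing is reported as missing; severe with missing is reported as severe.

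**Does one rationale explain both cut-offs?** Suppose the rationale is that an ungraded event might be worse than the graded one. Only the top level of a scale is then safe from being overridden. In 9.1.1 that is severe, and severe is what the rule protects. In 9.1.3 it would be Grade 5 alone, yet Grade 4 is protected too, although an ungraded reaction could be Grade 5. So 9.1.3 already accepts that a sufficiently serious recorded grade should be shown even when something worse cannot be excluded. The remaining question is where to draw that line. Table 4's definition of Grade 3 covers tissue loss and reactions needing an operation, and the SAP gives no reason for drawing the line above it.

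**Size per affected participant.** Planned arm sizes are 24 active and 12 placebo (Protocol 9.2; SAP 3.2).

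- Active: 1/24 = 4.2%.
- Placebo: 1/12 = 8.3%.

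These are the shift in the Grade 3 row if one participant meets the condition. They do not estimate how often that will happen, and the documents give no ISR rate or missing-grade rate from which to estimate it.

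**The case against.** **The trigger is narrow.** Under Protocol 10.3.3 a late injection-site sign is recorded as an ISR only if it meets a CTCAE criterion, and it is then graded from Table 4. An ungraded ISR is therefore a data gap, and SAP 4.3 provides for data cleaning and blinded review before lock. The same participant must also have a graded ISR under the same SOC and PT; a lone Grade 3 is reported as Grade 3. This stands, and it is why the point is minor.

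**Missing may be worse than Grade 3.** Severe is the top of a three-level scale, Grade 3 the middle of five, and no passage maps one to the other. That is correct, so a reader should not infer that 9.1.3 breaks a formal equivalence between Grade 3 and severe; the comparison rests only on the content of Table 4. But the argument does not justify the cut-off, because the rule already protects Grade 4.

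**The event is visible elsewhere.** SAP 9.1.3 states that "By-participant data listings for injection site reactions, treatment-emergent signs of muscle weakness or pain, and treatment-emergent kidney stones will be provided". The participant also remains in the ISR incidence counts, and the missing row itself signals unresolved severity. This stands: nothing disappears from the report. A listing does not, however, correct the summary row. The SAE tables are not a sure backstop either, since Protocol 10.3.4 keeps severity and seriousness apart.

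**Two stronger readings are tempting.** One is that six dosing visits make repeat reactions in a participant expected. The documents support only that repeats are possible. The other is that the loss would fall mainly on the active arm. No passage gives ISR frequency by arm, so the direction is unknown.

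**Conclusion.** The point holds as a minor defect in one descriptive safety table. Read literally, SAP 9.1.3 reports a participant with an ungraded and a Grade 3 ISR under the same SOC and PT as missing, against the worst-severity principle of 9.1.1. Each such participant moves the Grade 3 row by 4.2 percentage points in the active arm or 8.3 in placebo, assuming the safety population matches the planned 24 and 12.

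The case should be rare. The documents do not support reading this as a likely event, as a bias favouring one arm, or as concealment of the reaction from the study report. Grades 1 and 2 are overridden as well, but that parallels the handling of mild and moderate in 9.1.1 and is of less consequence.

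**What to change.** Either of two edits to SAP 9.1.3 would do:

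1. Extend the exception to Grade 3, Grade 4 or Grade 5. This is the smallest change and leaves the handling of Grades 1 and 2 as it is.
2. Report the highest recorded grade, use missing only when no grade was recorded, and add a separate line counting participants with any ungraded ISR. The extra line is needed: the highest recorded grade alone would treat the ungraded reaction as no worse, which could itself understate severity.

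The same edit can remove the repeated word in the sentence that opens the rule. The cost is a few words and, for the second option, one more table row. Neither needs new data or alters study conduct. The change is best made before unblinding, so that it cannot look like a response to the results.

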## 9.2. Clinical Laboratory Evaluations

Descriptive summaries for safety laboratory assessments will be presented at each visit starting at baseline. Changes from baseline to each post baseline visit will also be presented for continuous outcomes.

Baseline for safety laboratory assessments will be identified as defined in Section 6.1.2 regardless of whether an evaluation was scheduled, retested, or unscheduled. Since laboratory retests can occur for individual parameters, it will be necessary to define the baseline and all subsequent visit-specific laboratory values individually for each parameter.

[figure not shown]
In the case where below the limit of quantitation (BLQ) results are observed, and the LLOQ value is known, the BLQ values will be included in the numeric summary as the reported LLOQ value. In for those lab results reported as '<x' where x is numeric value, descriptive summaries will impute x as the lab result.

The following imputation rules will be applied to safety laboratory results where LLOQ value is unknown:

[figure not shown]
- If the patient has quantifiable concentrations of that analyte from other study visits, BLQ results will be imputed as  $\frac{1}{2}$  of the patient's lowest concentration for that analyte
- If the patient does NOT have any quantifiable concentrations of that analyte from other study visits, BLQ results will be imputed as  $\frac{1}{2}$  of the lowest concentration of that analyte based on all quantifiable results within the patient's dosing group/cohort

By visit summary tables will be presented for each category of data separately. Routine clinical laboratory data will include hematology, clinical chemistry, coagulation parameters, and urinalysis. Total complement (hemolytic activity and factors) will be reported similarly but will include reporting of the first quartile and third quartile in presentations; these summaries of total complement will be based on the log-transformed values. Shift tables for baseline to maximum and minimum post baseline values, based on laboratory normal ranges (below lower limit of normal [LLN], normal, above upper limit of normal [ULN]), will be provided for hematology, coagulation, complement, cytokines and clinical chemistry parameters. This analysis of extreme value shifts (e.g., maximum and minimum post baseline values) will be based on all post baseline assessments whether scheduled or unscheduled. The set of laboratory parameters included in each table will correspond to the study protocol.

The number and percentage of potentially clinically significant (PCS) laboratory values will be tabulated by laboratory parameter: the summary will indicate the number of participants with PCS-low or PCS-high values at any time post baseline, as identified in Table 3 and Table 4. This

[figure not shown]
analysis will be based on all post baseline assessments whether scheduled or unscheduled. It is possible for participants to appear in both categories (PCS-low and PCS-high) for any parameter.

**Table 3: Potentially Clinically Significant Criteria for Safety Laboratory Assessments for Participants  $\geq$  18 Years of Age**

| Parameter            | Units       | PCS Low | PCS High     | Sex |
|----------------------|-------------|---------|--------------|-----|
| Hemoglobin           | g/L         | <95     | -            | F   |
|                      | g/L         | <115    | -            | M   |
| Hematocrit           | %           | <32     | -            | F   |
|                      | %           | <37     | -            | M   |
| RBC count            | $10^{12}/L$ | -       | >10          | F   |
|                      | $10^{12}/L$ | -       | >8           | M   |
| WBC count            | $10^9/L$    | <2.8    | >16          | B   |
| Neutrophils (total)  | $10^9/L$    | <1.5    | $\geq 13.0$  | B   |
| Lymphocytes          | %           | -       | $\geq 75$    | B   |
| Monocytes            | %           | -       | $\geq 15$    | B   |
| Eosinophils          | %           | -       | $\geq 10$    | B   |
| Basophils            | %           | -       | $\geq 10$    | B   |
| Platelet count       | $10^9/L$    | <75     | >700         | B   |
| BUN                  | mmol/L      | -       | $\geq 10.71$ | B   |
| Serum creatinine     | umol/L      | -       | $\geq 176.8$ | B   |
| Total bilirubin      | umol/L      | -       | $\geq 34.2$  | B   |
| Alkaline phosphatase | U/L         | -       | >390         | B   |
| AST                  | U/L         | -       | >150         | B   |
| ALT                  | U/L         | -       | >165         | B   |

Abbreviations: ALT= alanine aminotransferase; AST= aspartate aminotransferase; B= both; BUN= blood urea nitrogen; F= female; HDL= high density lipoprotein; LDL= low density lipoprotein; M= male; PCS = potentially clinically significant; RBC= red blood cell; WBC= white blood cell

**Table 4: Potentially Clinically Significant Criteria for Safety Laboratory Assessments for Participants < 18 Years of Age**

| Parameter                    | Units               | PCS Low | PCS High | Sex |
|------------------------------|---------------------|---------|----------|-----|
| Hemoglobin (5y to 14y)       | g/L                 | <114    | >151     | B   |
| Hemoglobin (15y to 17y)      | g/L                 | <135    | >175     | M   |
| Hemoglobin (15y to 17y)      | g/L                 | <120    | >160     | F   |
| Hematocrit (5y to 14y)       | %                   | <36     | >47      | B   |
| Hematocrit (15y to 17y)      | %                   | <40     | >52      | M   |
| Hematocrit (15y to 17y)      | %                   | <36     | >46      | F   |
| RBC count (5y to 14y)        | 10  /L | <4.0    | >5.6     | B   |
| RBC count (15y to 17y)       | 10  /L | <4.6    | >5.8     | M   |
| RBC count (15y to 17y)       | 10  /L | <4.1    | >5.2     | F   |
| WBC count (5y to 17y)        | 10  /L  | <4.0    | >10.7    | B   |
| Neutrophils (Abs; 2y to 6y)  | 10  /L  | <2.1    | >8.9     | B   |
| Neutrophils (Abs; 7y to 17y) | 10  /L  | <1.6    | >7.4     | B   |
| Lymphocytes (2y to 6y)       | %                   | <16     | >60      | B   |
| Lymphocytes (7y to 12y)      | %                   | <12     | >49      | B   |
| Lymphocytes (13y to 17y)     | %                   | <20     | >44      | B   |
| Monocytes (2y to 6y)         | %                   | <3      | >8       | B   |
| Monocytes (7y to 17y)        | %                   | <3      | >10      | B   |
| Eosinophils (183days to 6y)  | %                   | -       | >4       | B   |
| Eosinophils (7y to 12y)      | %                   | -       | >6       | B   |
| Eosinophils (13y to 17y)     | %                   | -       | >7       | B   |
| Basophils (31days to 17y)    | %                   | -       | >2       | B   |
| Platelet count (5y to 14y)   | 10  /L  | <175    | >420     | B   |
| Platelet count (15y to 17y)  | 10  /L  | <150    | >350     | B   |
| Urea (0y to 9y)              | mmol/L              | -       | >5.712   | B   |
| Urea (10y to 15y)            | mmol/L              | -       | >6.426   | B   |
| Urea (16y to 17y)            | mmol/L              | -       | >7.14    | B   |

|                                   |        |   |         |   |
|-----------------------------------|--------|---|---------|---|
| Serum creatinine (4y to 12y)      | umol/L | - | >68.068 | B |
| Serum creatinine (13y to 17y)     | umol/L | - | >106.08 | M |
| Serum creatinine (13y to 17y)     | umol/L | - | >88.4   | F |
| Total bilirubin (8days to 17y)    | umol/L | - | >20.52  | B |
| Alkaline phosphatase (1y to 12y)  | U/L    | - | >299    | B |
| Alkaline phosphatase (13y to 17y) | U/L    | - | >389    | M |
| Alkaline phosphatase (13y to 17y) | U/L    | - | >186    | F |
| AST (4y to 6y)                    | U/L    | - | >47     | M |
| AST (4y to 6y)                    | U/L    | - | >58     | F |
| AST (7y to 17y)                   | U/L    | - | >41     | B |
| ALT (0y to 9y)                    | U/L    | - | >30     | B |
| ALT (10y to 17y)                  | U/L    | - | >30     | M |
| ALT (10y to 17y)                  | U/L    | - | >20     | F |

Abbreviations: ALT= alanine aminotransferase; AST= aspartate aminotransferase; B= both; BUN= blood urea nitrogen; F= female; M= male; PCS = potentially clinically significant; RBC= red blood cell; WBC= white blood cell

[figure not shown]
Results of urine pregnancy tests (females only) will be presented in a listing only. Viral serology data and anti-drug antibody tests will be handled similarly.

Data listings for all laboratory results will be generated. Where appropriate, assessments considered to be PCS will be noted; abnormal values (e.g., above the upper limit of normal or below the lower limit of normal) will be identified. A separate listing of PCS safety laboratory data will be provided.

Participant data listings will include the type of visit (e.g., scheduled test, retest, unscheduled), age, sex, laboratory test, test units, laboratory test result, and the laboratory standard normal ranges adjusted as appropriate for age and sex, if available.

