5. STUDY POPULATION

5.1. INCLUSION CRITERIA

In order to be eligible to participate in this study, an individual must meet all of the following criteria:

Age

1. At least 6 years of age, at the time of signing the informed consent/assent

Type of Participant and Disease Characteristics

2. Documented diagnosis of PH1 or PH2, confirmed by genotyping (historically available genotype information is acceptable for study eligibility)
3. 24-hour Uox excretion ≥ 0.7 mmol (adjusted per 1.73 m^2 BSA in participants < 18 years of age) in both collections performed in the screening period. At least 12 participants must have at least one 24-hour Uox excretion ≥ 1.6 mmol (adjusted per 1.73 m^2 BSA in participants aged < 18 years).
4. Less than 20% variation between the two 24-hour urinary creatinine excretion values obtained in the screening period. Individuals who do not achieve $< 20\%$ variation between the 2 screening values may undergo a second round of urine collection. An extra 7 calendar days may be added to the screening window for participants to complete a second round of urine collection. Should potential participants again fail to achieve the within-20% variation, they will be excluded from participation.
5. Estimated GFR at screening ≥ 30 mL/min normalized to 1.73 m^2 BSA, calculated using the CKD-EPI equation in participants aged ≥ 18 years ([Levey & Stevens, 2010](#)) or the multivariate equation by Schwartz in participants aged 6 to 17 years ([Schwartz et al., 2012](#))

Sex

6. Male or female

Male participants:

A male participant with a female partner of childbearing potential must agree to use contraception, as detailed in Section 10.4.2, during the treatment period and for at least 12 weeks after the last dose of study intervention and refrain from donating sperm during this period.

Female participants:

A female participant is eligible to participate if she is not pregnant (see Section 10.4.1), not breastfeeding, and at least 1 of the following conditions applies:

Not a woman of childbearing potential (WOCBP) as defined in Section 10.4.1

OR

A WOCBP who agrees to follow the contraceptive guidance in Section 10.4.2 during the treatment period and for at least 12 weeks after the last dose of study intervention.

Contraceptive use by men or women should be consistent with local regulations regarding the methods of contraception for those participating in clinical studies.

Informed Consent/Assent

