**Table 5: Potentially Clinically Significant Criteria for Vital Signs for Participants ≥ 18 Years of Age**

| Vital sign               | Criteria  |
|--------------------------|---|
| Heart Rate               | ≥120 bpm at any time post dose and ≥15 bpm increase from baseline     |
|                          | ≤50 bpm at any time post dose and ≥15 bpm decrease from baseline      |
| Systolic blood pressure  | ≥180 mm Hg at any time post dose and ≥20 mm Hg increase from baseline |
|                          | ≤90 mm Hg at any time post dose and ≥20 mm Hg decrease from baseline  |
| Diastolic blood pressure | ≥105 mm Hg at any time post dose and ≥15 mm Hg increase from baseline |
|                          | ≤50 mm Hg at any time post dose and ≥15 mm Hg decrease from baseline  |

Abbreviations: bpm = beats per minute; mm Hg = millimeters mercury

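### The laboratory PCS count ignores baseline and does not separate children from adults, so renal impairment present at entry is reported as a post-baseline finding

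*SAP*

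**What the plan says.** SAP section 9.2 tabulates, by laboratory parameter, the number and percentage of participants with "PCS-low or PCS-high values at any time post baseline, as identified in Table 3 and Table 4". It adds that the "analysis will be based on all post baseline assessments whether scheduled or unscheduled". Table 3 gives the cut-offs for adults and Table 4 those for participants under 18. Both are absolute values, and neither carries a baseline or change condition.

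Rows of Table 4 that matter here include "Serum creatinine (4y to 12y) | umol/L | - | >68.068 | B", "ALT (10y to 17y) | U/L | - | >20 | F" and "AST (7y to 17y) | U/L | - | >41 | B". The corresponding adult limits in Table 3 are 176.8 umol/L or more, above 165 U/L and above 150 U/L.

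Other PCS criteria in the same SAP do use baseline. Each vital-sign rule in Tables 5 and 6 pairs a level with a minimum change. The adult heart-rate rule, for example, reads "bpm at any time post dose and" and continues with a change of at least 15 bpm from baseline. The ECG heart-rate rules in Tables 7 and 8 do the same.

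On eligibility, the renal criterion in Protocol 5.1 ("Estimated GFR at screening") is met at 30 mL/min per 1.73 m² or above. Protocol 5.2 excludes ALT or AST only above 1.5 times the upper limit of normal (ULN).

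**The concern.** A PCS table in a placebo-controlled trial is read as a list of things that happened after treatment began. Under this rule a participant who entered with reduced kidney function and never changed is listed beside one whose creatinine rose on study. Reduced kidney function is expected in this disease and permitted by the entry criteria, so the situation is foreseeable.

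The second difficulty is that one table serves two very different scales. A child's ALT just over 20 or 30 U/L and an adult's ALT over 165 U/L both count as one PCS-high participant. Section 9.2 does not say that the two age groups are shown apart, and SAP 4.1 makes summaries by treatment and overall the default. Children aged 6 to 11 are the group most recently opened to enrolment, so a PCS count that cannot be interpreted matters most there.

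**Working it through.** The documents state no expected PCS rate, so there is no planned figure to reproduce. The checks use the plan's own cut-offs and equations.

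**1. Creatinine cut-offs in children, expressed as eGFR.** The equation is Schwartz 2009 (Protocol 8.2.4.1, SAP 6.1.9), which the plan uses for its main paediatric eGFR analysis: eGFR = 36.5 × height in cm ÷ serum creatinine in umol/L. Heights are assumed.

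- Ages 4–12, cut-off 68.068, height 115 cm: 36.5 × 115 ÷ 68.068 = 61.7
- Ages 4–12, cut-off 68.068, height 150 cm: 36.5 × 150 ÷ 68.068 = 80.4
- Boys 13–17, cut-off 106.08, height 165 cm: 36.5 × 165 ÷ 106.08 = 56.8
- Girls 13–17, cut-off 88.4, height 160 cm: 36.5 × 160 ÷ 88.4 = 66.1

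A child whose eGFR on this equation is between 30 and the value shown has a creatinine above the cut-off before the first dose.

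**2. The same check with the current entry equation.** Paediatric eligibility now uses Schwartz 2012, which also needs cystatin C and urea nitrogen. Take creatinine 68.068 umol/L (0.77 mg/dL) and height 1.15 m, and assume urea nitrogen 15 mg/dL and cystatin C 0.8 to 1.5 mg/L. The result is about 53 (girl, cystatin C 1.5) to 74 (boy, cystatin C 0.8). The whole range is above 30, so a child at the cut-off remains eligible.

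**3. Creatinine cut-off in adults.** Table 3's 176.8 umol/L is 176.8 ÷ 88.4 = 2.0 mg/dL. CKD-EPI is both the entry and the analysis equation for adults.

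- Non-Black man aged 30: 141 × (2.0/0.9)^−1.209 × 0.993^30 = 43.5
- Non-Black woman aged 30: 141 × (2.0/0.7)^−1.209 × 0.993^30 × 1.018 = 32.7

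For non-Black men aged 18 to 60 the value runs from 47.3 down to 35.2. An adult can therefore be eligible and already PCS-high, over a narrower eGFR range than a child.

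**4. Table 4 against Table 3** (adult cut-off ÷ child cut-off):

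- ALT: 165 ÷ 20 = 8.25 (girls 10–17); 165 ÷ 30 = 5.5 (boys 10–17 and all children to age 9)
- AST, ages 7–17: 150 ÷ 41 = 3.7
- Creatinine, ages 4–12: 176.8 ÷ 68.068 = 2.6
- Bilirubin: 34.2 ÷ 20.52 = 1.7

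**5. Table 4 against the protocol's liver alert.** For participants with normal liver tests at baseline, Protocol 7.1.1 starts close monitoring when ALT or AST exceeds 3 × ULN. The adult cut-offs equal 3 × ULN if the ULN is 165 ÷ 3 = 55 (ALT) and 150 ÷ 3 = 50 (AST). The child cut-offs would equal it only if the ULN were 20 ÷ 3 = 6.7, 30 ÷ 3 = 10 (ALT) and 41 ÷ 3 = 13.7 (AST). A child may also enter already above the Table 4 limit if the ULN exceeds 20 ÷ 1.5 = 13.3, 30 ÷ 1.5 = 20 (ALT) or 41 ÷ 1.5 = 27.3 (AST).

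**The case against.** The strongest reply is that the PCS table is one descriptive output among several. Section 9.2 also plans change from baseline by visit, shift tables from baseline to the post-baseline extremes, and listings with actual values and normal ranges. Protocol 7.1.1 adds real-time liver alerts, and the DSMC sees unblinded data. The placebo arm shows the background rate, and minimization balances age group and eGFR category. All of this stands. It rules out the inference that a true laboratory signal would be hidden from the trial. It does not make the PCS table interpretable. The shift tables have three categories, so they do not grade values above the ULN, and no table by multiples of ULN is planned. Minimization splits eGFR at 45, below the 57 to 80 at which the child creatinine limits fall.

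A reader might also infer that nearly every child will be flagged whatever the treatment, or that children's flags will swamp those of adults. The documents support neither. PCS is tabulated per parameter, with no any-flag statistic, and the number of children is not given. Nor is it established that Table 4 reproduces laboratory normal limits. Its age bands suggest as much, but no normal ranges are printed.

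Absolute-only flags are not unique to the laboratory tables: the QRS criteria are absolute, and the QTcF criteria accept either a level or a change. A sensitive screen in children is also a defensible choice. These points argue against prescribing new cut-offs. They do not argue against showing baseline status and age group.

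**Conclusion.** The point holds as a limited defect in the PCS table and listing. The laboratory rule takes no account of baseline, and the entry criteria admit participants who already meet it. For creatinine these are children with eGFR from 30 up to about 57 to 80, depending on age, sex and height, and, taking a non-Black man aged 30 as the example, men entering at 30 to about 43. They count as post-baseline PCS on either arm for as long as creatinine stays at that level. The child figures rest on assumed heights and the Schwartz 2009 equation; under Schwartz 2012 the limit also falls well above 30 in the case checked. How many participants are affected cannot be derived from the documents.

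Table 4 is far tighter than Table 3 and, for any plausible ULN, well below the protocol's 3 × ULN alert, so a count that mixes the two tables has no single meaning. The safety analyses are descriptive, so neither type I error nor power is touched. The change is worth making because it improves what the table can say about treatment and loses no flag.

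**What to change.** In SAP section 9.2, for each treatment arm and parameter:

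- Split the PCS count into participants not PCS at baseline (treatment-emergent) and participants already PCS at baseline, using the baseline already defined in SAP 6.1.2.
- Keep the second group in the table and listing with their change from baseline. Simply excluding them would drop a participant with renal impairment who worsens.
- Report participants under 18 (Table 4) and adults (Table 3) separately.

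The sponsor should also reconcile the level of the Table 4 cut-offs with Table 3 and with the liver alert in Protocol 7.1.1, or state why they differ. No cut-off is proposed here.

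The baseline split resolves findings fixed at entry but only partly reduces chance flags. As an illustration, assume 2.5% of untreated values lie beyond a limit and use the 10 scheduled post-baseline draws. Counting only those not PCS at baseline then lowers the no-effect rate per limit from 22.4% to 21.9% if visits are uncorrelated, and from 5.0% to 2.6% at a within-person correlation of 0.95. That is why the cut-off levels need their own reconciliation.

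The cost is SAP wording and table programming before database lock. No new data, visits or participants are needed.
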